13 STUDY INTERVENTION DISCONTINUATION AND PARTICIPANT DISCONTINUATION/WITHDRAWAL

13.1 DISCONTINUATION OF STUDY INTERVENTION

A small proportion of participants may find the headset uncomfortable, the VR experiences ineffective, or find themselves not using the device and wish to withdraw. Participants who report moderate to severe adverse events that prevent them from using the program will be discontinued. Discontinuation from the use of the VR program or Sham VR will not automatically trigger discontinuation from the study, and remaining study procedures should be completed as indicated by the study protocol. If a clinically significant finding is identified (including, but not limited to changes from baseline) after enrollment, the investigator or qualified designee will determine if any change in participant management is needed. Any new clinically relevant finding will be recorded as an adverse event (AE).

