13.2 PARTICIPANT DISCONTINUATION/WITHDRAWAL FROM THE STUDY

Participants are free to withdraw from participation in the study at any time and for any reason. A member of the research team will ask the participant for the reason for their withdrawal and will record all information regarding the participant discontinuation in their study records.

An investigator may also discontinue or withdraw a participant from the study for the following reasons:

- If any serious to severe adverse event (AE) or other medical condition or situation occurs such that continued participation in the study would not be in the best interest of the participant
 - Participants who experience an SAE due to an undisclosed condition that would have prevented trial eligibility will be discontinued from the study and will be documented as an eligibility deviation.
- Disease progression which requires discontinuation of the study intervention
- If the participant meets an exclusion criterion (either newly developed or not previously recognized) that precludes further study participation
- Any other problem deemed by the Investigator to be sufficient to cause discontinuation.

The reason for participant discontinuation from the study will be recorded.

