1.8.2 MODIFIED INTENT TO TREAT ANALYSIS SET (mITT)

For the primary analysis and safety evaluations, the mITT Analysis Set will be defined and presented as primary. The mITT Analysis Set includes all enrolled subjects who actually receive the device. If all enrolled subjects receive the device, the mITT and ITT Analysis Sets will coincide and will be referred to as the ITT Analysis Set.

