3.2 SAFETY ANALYSIS

Assessment of the safety of the investigational device will include an evaluation of the incidence and severity of complications and adverse reactions associated with the treatment. Primary safety comparisons will be performed using the mITT analysis set.

Adverse event rates will be summarized by type of AE and for specific AEs in two ways:

1. Per subject incidence of specific AEs and classes of AEs
2. By event, summarizing event counts by visit interval over time and in accordance with FDA Guidance (CDRH 2004).

Events will be summarized by severity and relatedness.

The summary tables will show the adverse events (in coded terms), the total number of events, and the number and the percentage of subjects affected in the investigational group

(“subject wise evaluation”) and stratified by relation to device and severity. Data of dropouts will not be presented separately, but possible bias will be discussed in the final report.

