3.3 PROTOCOL DEVIATIONS

Protocol deviations will be summarized by experimental group.

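### SAP 3.2 words the subject-level adverse event tables for the investigational group alone, which conflicts with its own planned safety comparisons and, read literally, drops the sham column

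*SAP*

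**What the plan says.** SAP 3.2 (Safety Analysis) is the only section that specifies the AE tables. It opens with the comparison: "Primary safety comparisons will be performed using the mITT analysis set". SAP 1.8.2 defines that set: "The mITT Analysis Set includes all enrolled subjects who actually receive the device". SAP 3.2 then lists two kinds of summary, one per subject and one per event, without naming an arm. Its last paragraph describes the tables themselves: coded terms, total events, and "the number and the percentage of subjects affected in the investigational group", broken down by relatedness and severity. It closes with "Data of dropouts will not be presented separately, but possible bias will be discussed in the final report".

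The next section, SAP 3.3, states its grouping outright: "Protocol deviations will be summarized by experimental group".

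On stopping because of AEs, Protocol 13.1 says "Participants who report moderate to severe adverse events that prevent them from using the program will be discontinued" and also "Discontinuation from the use of the VR program or Sham VR will not automatically trigger discontinuation from the study". For people who leave the study, Protocol 13.2 says "The reason for participant discontinuation from the study will be recorded".

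**The concern.** A programmer who builds table shells from SAP 3.2 has two instructions that cannot both be followed: compare safety in a set that contains both treatments, and tabulate affected subjects for one of them.

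The sham column matters because of the design. Protocol 7.4 gives sham participants the same headset with non-immersive content. The difference between arms is therefore what separates symptoms due to the EaseVRx content from symptoms due to wearing the headset, and from background complaints in people with chronic back pain followed for two years. Without sham percentages beside them, the EaseVRx percentages cannot be read in that way.

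**Working it through.** The plan gives no safety figure to reproduce, so the main check sets the passages side by side.

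1. **Does the table phrase mean everyone in the trial?** SAP 1.2 sets the investigational product, EaseVRx, against the control, ShamVR. SAP 2.3 and 2.9.1 draw the same contrast for the device. The natural reading of the table phrase is therefore EaseVRx only.

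2. **Does the safety set contain sham participants?** SAP 1.8.2 admits all enrolled subjects who receive the device and uses the same set for the primary analysis, which compares EaseVRx with Sham. SAP 1.3 calls the sham a device as well. So yes.

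3. **Does other text settle the conflict?** The per-subject incidence item in SAP 3.2 names no arm, so it neither restricts nor guarantees a sham column. SAP 2.1 promises descriptive summaries in all four groups, but for primary and secondary endpoints, not AEs. SAP 3.3 concerns deviations only. Nothing states that AEs are tabulated by arm.

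4. **Over what period is pooling sound?** SAP 2.2 pools the two EaseVRx arms and the two Sham arms because they differ only after week 8. Protocol 16.4 collects AEs through the final follow-up visit, and Protocol 7.5 gives two of the four arms optional headset use in weeks 9 to 16. Pooled AE tables are justified through Day 56. After that they would mix 8-week and 16-week access.

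5. **Illustration of what a sham column adds.** Every rate here is an assumption. The only related figure in the documents is Protocol 7.7.1, where fewer than 10% in earlier research had cybersickness that prevented use. No safety test is planned, and the figures show precision, not bias. Take n = 1000/2 = 500 per pooled arm, assuming all enrolled participants receive the device.

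- One arm: half-width = 1.96 × √(p(1−p)/n). For p = 5%: 1.96 × √(0.05 × 0.95/500) = 1.9 points.
- Difference: half-width = 1.96 × √(p₁(1−p₁)/n + p₂(1−p₂)/n).

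| EaseVRx | Sham | Difference (points) | Half-width (points) |
|---|---|---|---|
| 5% | 1% | 4 | 2.1 |
| 5% | 2% | 3 | 2.3 |
| 5% | 5% | 0 | 2.7 |
| 10% | 2% | 8 | 2.9 |

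An EaseVRx figure of 5% shown alone is compatible with any of the first three rows.

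**The case against.** The strongest reply is that this is one loose sentence. The section commits to safety comparisons, the safety set includes Sham, and the per-subject incidence item is not limited to EaseVRx, so a sensible team would produce both columns. That is fair, and it limits the point to a correction of wording. It does not remove it, because the loose sentence is the one that specifies the table content. The illustration proves no error either: that a single-arm rate fits many sham rates is true in any trial.

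A reader might infer three stronger things, none of which the documents support.

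- *That the sponsor intends a one-arm safety report.* The planned comparisons in SAP 3.2 point the other way.
- *That the sentence on dropouts hides AEs in people who stop.* It says only that their data get no separate presentation. Anyone who received the device stays in the mITT set.
- *That the lack of a stated by-arm table of AEs leading to device discontinuation or study withdrawal is an error.* No section promises that table, but much of the ground is covered. Protocol 13.2 records reasons for leaving the study. Protocol 14.1 includes a Discontinuation of Treatment Questionnaire for use after a moderate AE. SAP 2.9.2 says that reasons for discontinuation will be assessed. The accounting table in SAP 3.1 is a minimum list, and the guidance that it follows is not among these documents. Protocol 16.2 defines the Severe grade partly by symptoms that prevent further headset use, so once the phrase is corrected the planned severity rows carry part of this information by arm. The Severe row is not an exact substitute: it also takes in functional limitation, and some Moderate events may lead to stopping.

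**Conclusion.** The point holds as an internal inconsistency in SAP 3.2 that is worth correcting. The table sentence names one treatment group, while the section's own comparisons need two. If the sentence were followed literally, the subject-level AE tables would lack the same-headset comparator.

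The size is that of a reporting defect. No sample size, power, alpha or efficacy estimate changes, and no numerical bias can be claimed. The conclusion rests on reading the word investigational as the SAP uses it elsewhere, and on the available text: the table shells, the eCRF and the cited guidance could not be checked.

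**What to change.** In SAP 3.2, change the phrase so that the number and percentage of affected subjects are given in each experimental group. Specify pooled EaseVRx against pooled Sham for AEs through Day 56, and the four randomized arms for later AEs. Show the existing severity and relatedness rows by arm. Keep the commitment to discuss possible bias from dropouts.

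Optionally, add a by-arm count of AEs leading to device discontinuation and to study withdrawal, built from the recorded reasons and the discontinuation questionnaire. For weeks 9 to 16 it would need a definition of device discontinuation, because use is then voluntary.

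The cost is one phrase and slightly larger tables, with no extra participants, visits or tests. The tolerability picture may look less favourable to EaseVRx once sham stands beside it.

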3.3 PROTOCOL DEVIATIONS

Protocol deviations will be summarized by experimental group.

3.4 SOFTWARE FOR DATA ANALYSIS

Analysis will be performed with SAS® software Package (Release 9.4 or higher) or R (version 4.1 or higher).

3.5 CHANGES TO THE ANALYSIS PLAN

All Changes to the Analysis Plan will be documented in the Clinical Study Report. Deviations to the analysis plan will be described in full in at least a supplemental section for publications.

